## Measures and Data Collection

### Overview

Measurement will occur at baseline, 6 months (at the completion of the intervention), and 12 months after enrollment. Variables chosen for measurement are based on our conceptual framework (Section 3.4.1). At baseline, 6 months, and 12 months, patients (participants and peer mentors) will complete a written survey and assessments of A1c and blood pressure. Patients will receive \$25 for each assessment they complete. To understand features of successful vs. less successful peer partnerships, we will conduct semi-structured telephone interviews at 6 months of a purposive sample of participants and mentors in both study arms (choosing a sample with high rates of contact and a sample with low rates of contact). Using standard qualitative methods for identifying key themes in participant's experiences with this new program, we will identify central themes from these interviews associated with the success of the peer relationships and in meeting intervention goals. Participants and peer mentors in the peer mentor +iDecide arm will be asked about their experiences with iDecide and how use of the program affected their subsequent contacts and activities (e.g., setting and meeting 'action plan' goals, effectively raising questions and concerns with PCPs). Quantitative information about use of the IVR system will be collected via computerized records that the system maintains of all contacts with dates and time durations of all contacts as well as of attempted contacts. To assess peer mentors' experiences, we will conduct semi-structured interviews with a purposive sample of peer mentors with differing rates of participation (e.g., those who made regular contact with their assigned peers vs. those who did not).

### 3.6.2 Description of Measures by Aim

**Aim 1:** Test the effectiveness of a technology-enhanced peer coaching (TEC) program in improving glucose control relative to peer support alone. At baseline, 6 months, and 12 months, a trained staff member will measure patients' A1c, using a Bayer DCA 2000+ analyzer, a portable analyzer producing A1c assays in approximately six minutes using finger stick blood samples. These assays have a test coefficient of variation (CV, measure of test precision) <5% as required by the National Diabetes Data Group and accurately measure A1c levels.[78] The DCA 2000 is reliable, easy to use, and much less burdensome to patients than venous blood draws. Our team has familiarity with the DCA 2000 from our prior studies.[40,56] To ensure quality control, venous A1c samples will be drawn from 5% of participants and analyzed at the Detroit VA's lab.

For our "usual care" observed group, we will use CDW data to measure A1c levels. More than 85% of diabetes patients who meet our eligibility criteria receive A1c testing at recommended intervals, which should ensure adequate numbers of patients with follow-up A1c levels in our control sample. For those with missing A1c data, we will use several approaches to examine possible biases (see section 3.7.5).

**Aim 2:** Assess the impact of the intervention on blood pressure and medication adherence as well as on key patient-centered outcomes, including patients' satisfaction and involvement with care, perceived social support, and diabetes-specific quality of life. These measures will be assessed at baseline, 6 months, and 12 months. We will measure blood pressure using an Omron® automatic blood pressure

monitor with memory and take the average of the two readings following American Heart Association guidelines. (Ideally we would also measure lipid levels, but have not found sufficiently reliable point-of-service machines for these measurements. At baseline we will collect information on most recent LDL, HDL, and total cholesterol levels from electronic medical records. If there are no recent values, the iDecide program text in that section will emphasize the importance of having these risk factor levels checked.) The baseline and 6-month surveys will take approximately 25 minutes to complete, and the 12-month survey will take approximately 15 minutes. Measures for the key patient-centered outcomes are:

The Health-Care Climate Questionnaire (HCCQ) (twelve items). The Health-Care Climate Questionnaire (HCCQ) ( $\alpha=0.82$ ) assesses patients' perceptions of the degree to which they experience their health-care providers (or their peer mentor) to be autonomy supportive versus controlling in providing general health support or with respect to a specific health-care issue. It was originally validated in a study of patients visiting their primary-care physicians, was used in a published study of obese patients participating in a weight-loss program, has since been used in multiple studies of professional and lay health care supporters, and a version that includes six items measuring practical support for diabetes self-management has since been validated in two studies. [79] We will ask participants to complete this about their PCP at baseline, six-months, and 12-months. Participants will complete this assessment about their peer mentor at six months.

Involvement in Care Decisions (five items). To assess changes in how involved patients feel they are in diabetes goal and treatment decision-making with their health care providers, we will use the goal-setting subscale of the Patient Assessment of Chronic Illness Care (PACIC).[80]

Diabetes-Specific Social Support (twelve items). To assess perceived diabetes-specific support we will use the Diabetes Support Scale (DSS), a 12-item scale developed to assess whether an Internet-based diabetes support group changed participants' perceptions of social support, social network size, or actual provision of support ( $\alpha> 0.90$ ). The instrument correlates with illness intrusiveness and self-care behaviors and is responsive to intervention effects.[81]

Diabetes-Specific Distress (two items). This instrument captures the patient's perspective on the emotional burden of diabetes and its treatment.[82] It has consistently high internal reliability with a Cronbach's  $\alpha$  of 0.90 and good convergent validity with a measure of general psychological distress ( $r=.63$ ). It is also associated with changes in A1c and other outcomes over time. In a review of seven effective diabetes intervention studies, mean scores improved from baseline to follow up in all studies.[83]

Aim 3: Identify patient characteristics associated with engagement in the intervention and mediators and moderators of the intervention's impact on patient outcomes.

Table 2 presents the measures we will use to assess factors we hypothesize may be associated with willingness to engage in the intervention (which may also be moderators) and mediators and

moderators of intervention effects as well as time points at which we will measure each of these. We include measures found to be significant mediators and moderators of effects in our P2P RCT.[40,84]

Mediators      Time Points\*      Original Source

Medication-taking Self-efficacy    1, 2      Perceived Competence Scale[85]

Autonomous Motivation      1, 2      Treatment Self-Regulation Questionnaire (TSRQ[85])

Medication adherence    1,2      Morisky Medication Adherence Measure[86]

Assessment of level and type of support received by Peer coach    2      Process measures used in P2P and by Robert Wood Johnson Foundation Diabetes Initiative [40]

Self-efficacy for shared decision-making with providers    1,2      Self-efficacy for Decision-making scale[87]

Medication doses and insulin starts      1,2      Survey items and electronic medical records

Moderators/Engagement Factors

Race    1      2010 US Census measures

Preferred and actual decision-making with providers    1      Preferred and Actual Participation in Decision-making Scales[88]

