Attachment Style      1      Relationship Questionnaire[89]

Perceived Need for DM self-management support      1      Support Needs Scale from Diabetes Care Profile[90]

Perceived Benefits and Barriers to Taking DM medications      1      Two subscales from instrument assessing perceived barriers to and benefits from taking diabetes medications based on health beliefs model[91]

Health Literacy    1      Functional Health Literacy Screener[18]

Numeracy      1      Subjective Numeracy Scale (SNS)[92]

Food insecurity 1      Food Security Survey Module [93]

Neighborhood Safety, Availability of Healthy Foods, and Walking Environment 1      Neighborhood Safety Measure, Availability of Healthy Foods, Walking Environment [94]

\*Time point 1 is baseline, 2 is at 6 months, 3 is at 12 months.

We will measure standard demographic information including age, gender, and marital status. Socio-economic status (SES) will be measured using highest grade in school completed, income, and household size. We will collect data on diabetes duration and whether all diabetes care is received at VA and distance Veteran travels to Detroit VA. We will also collect data on any adverse symptoms experienced during the study period such as hypoglycemic symptoms or episodes, although have had no hypoglycemic episodes in our prior peer support interventions. Data on diabetes-related complications and other co-morbidities will be drawn from EMRs.

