We will follow international guidelines for analysis and reporting of clinical trials.[97] In the first phase (data verification), we will examine the distribution of all study variables to assess extreme values, missing data, variances, possible coding errors, skewness, and type of distribution. We will examine baseline data for clinically important differences across the two study groups for potential prognostic indicators, such as patients' age, race, comorbidities, and baseline use of services. Although we do not anticipate any imbalances due to the randomization, any differences between experimental arms in baseline characteristics will be included as covariates in analyses comparing outcomes. In the second phase of our outcomes analyses, we will evaluate possible bivariate associations between patients' experimental condition and the outcomes, as well as between each covariate and the outcomes, prior to fitting multivariable models. This will be done to determine unadjusted measures of effect, assess possible confounders, and anticipate any collinearity in subsequent analyses. In the final phase we will fit multivariable models to identify main effects.

Analysis Plans by Aim

Aim 1: Test the effectiveness of a technology-enhanced peer coaching (TEC) program in improving glucose control relative to peer support alone. Our past experience in similar patient populations

suggests that the primary endpoint from the trial (change in A1c) will be close to normally distributed. To assess the primary endpoint for Specific Aim 1 (change in mean HbA1c from baseline to 6 months), we will use a general linear mixed regression model:

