where i represents the patient, I represents the intervention, j is the pair-group, β_l are parameters estimated from the data, X_{il} is the value of the l th fixed effect (peer support versus usual care) for the i th patient, β_j are parameters estimated from the data, Z_{ij} is the value of the j th random effect (pairs) for the i th patient, and ϵ_i is the residual error.[99] We anticipate that members of peer coach-peer partner pairs in both arms, because of their interactions with each other, might show a positive intraclass correlation (ICC), a component of the variance attributable to the group. As recommended for group-randomized trials, the mixed model analyses will thus address potentially inflated type I errors that could occur if such clustering were not taken into account.[97] If patients in either arm drop out of the study or request reassignment to another peer coach, they will be analyzed according to their initial pairing in an intent-to-treat analysis.

After unadjusted changes in A1c are determined, further analyses using mixed-model ANCOVA will adjust for confounding effects of any variables that differed substantially between treatment arms. Both unadjusted and adjusted means with 95% confidence intervals will be reported for both arms. While the primary endpoint is the mean difference between baseline and 6-month A1c concentrations, subsequent analyses will be conducted to determine whether the intervention additionally affects the difference between baseline and 12-month A1c (i.e., the sustainability of any treatment effects) using a repeated-measures mixed model ANCOVA.

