We will follow the same approach to comparing the observed usual care group with the peer support alone group. However, there is a higher likelihood of imbalances as the usual care group is observational, although they are drawn from the same eligibility pool as the participants. Therefore, we will include several key covariates in the analysis, including baseline A1c, age, gender, and race. We will also examine the data for differences in other potential prognostic indicators, such as baseline medication or service use, and include these variables in the regression if necessary. We will also need to examine whether biases may be caused by missing A1c data. Although the very high level of A1c testing in VHA is likely to lead to few missing data points, we will conduct sensitivity analyses using two approaches. In the first, we will assume that those with missing A1c levels at the end of the study had no improvement in their A1cs. In the second, we will use multiple imputation methods to fill in missing A1c values.

Aim 2: Assess the impact of the intervention on blood pressure and medication adherence as well as on key patient-centered outcomes, including patients' satisfaction and involvement with care, perceived social support, and diabetes-specific quality of life. For assessment of changes in systolic blood pressure and for the self-reported outcomes, we will use mixed effects models (similar to those in Aims 1) for

continuous outcomes, and generalized estimating equations (GEE) for ordinal outcomes with clustering.[98]

Aim 3: Identify patient characteristics associated with engagement in the intervention and mediators and moderators of the intervention's impact on patient outcomes. For these analyses, we will use multivariate modeling and path analyses.[99] Many of these outcomes will be measured using Likert scales. Thus, we will begin these analyses by developing contingency tables for ordered categorical data. We will then use generalized estimating equations (GEE), which are appropriate for modeling ordinal outcomes with correlated data.[99]

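### Peer support alone versus usual care: A1c comes from scheduled study tests in one group and routine records in the other, so a companion analysis using routine records in both is worth adding

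*Protocol*

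**What the plan says.** The Protocol's Overview sets a fixed schedule for trial patients: "Measurement will occur at baseline, 6 months (at the completion of the intervention), and 12 months after enrollment". Section 3.6.2 (Aim 1) has a trained staff member run the test on a DCA 2000+ at each of those times, with venous samples from 5% of participants sent to the Detroit VA laboratory for quality control. For the usual-care group the same section says "we will use CDW data to measure A1c levels". It supports this with the statement that "More than 85% of diabetes patients who meet our eligibility criteria receive A1c testing at recommended intervals", and refers missing values to section 3.7.5.

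SAP 3.7 (Aim 1) defines the main endpoint as "change in mean HbA1c from baseline to 6 months". It adds a 12-month analysis: "subsequent analyses will be conducted to determine whether the intervention additionally affects the difference between baseline and 12-month A1c". It then says of the non-randomized contrast: "We will follow the same approach to comparing the observed usual care group with the peer support alone group". It recognises that usual care is observational. It names baseline A1c and three demographic covariates, allows others such as medication or service use if needed, and plans two sensitivity analyses for missing A1c (no improvement assumed, and multiple imputation). SAP 3.7.5 adds imputation within strata of the modelled likelihood of having outcome data.

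**The concern.** In this contrast every peer-support value is a scheduled study test, and every usual-care value is a test that routine care happened to generate and record. Group and A1c source coincide completely, so no covariate can separate them. A difference between the groups could reflect peer support, the assay, how far the recorded test lies from month 6 or 12, or some mixture of these. The comparison is already open to confounding because it is not randomized. The source difference is a further and avoidable ambiguity, and SAP 3.7 does not mention it when it lists the weaknesses of this comparison.

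**Working it through.** **The two groups side by side**

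| | Peer support alone | Usual care |
|---|---|---|
| Source | DCA, run by study staff | CDW record |
| Timing | Study visits at baseline, 6 and 12 months | Whenever routine care tested |
| Who has a value | Those attending the visit | Those tested within VA |

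**What each safeguard reaches**

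- *Named and optional covariates:* patient imbalance. Service use, if added, also bears on who gets tested. None adjusts for source or test date.
- *No-improvement, multiple-imputation and propensity-stratified analyses:* selection into having a value. They leave values that are present as they are.
- *Venous check:* assay agreement, but for quality control, with no stated use in the analysis. It covers 0.05 × 348 = 17.4, about 17 patients. Assume a 5% CV for each method (the Protocol says only that the DCA CV is below 5%). The SD of a paired difference is then 0.05 × A1c × √2, which is 0.566 at A1c 8 and 0.636 at A1c 9. The 95% half-width for the mean offset is 1.96 × SD/√17.4 = 0.27 to 0.30 points. A lower CV would narrow this in proportion.

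**Reproducing the plan's sample size.** SAP 3.7 gives a difference of 0.5, SD 1.45, two-sided alpha 0.05, 80% power and ICC 0.03, with 148 patients and 37 mentors per group. The unadjusted n is 2 × [1.45 × (1.960 + 0.842)/0.5]² = 132.0. With 148/37 = 4 patients per mentor, the design effect is 1 + 3 × 0.03 = 1.09 and n = 143.9. Counting the mentor in the cluster (5 members), it is 1.12 and n = 147.9, against 148 stated. For attrition, 148/0.85 = 174.1, against 174 stated. The inputs can be relied on.

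**Device offset, illustration only.** A constant offset d between sources cancels in a plain change score (d − d = 0). With baseline A1c as a covariate with slope B, d × (1 − B) remains. Assume d = 0.2:

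- B = 0.8: 0.2 × 0.2 = 0.04, which is 8% of the 0.5 design difference.
- B = 0.5: 0.2 × 0.5 = 0.10, which is 20% of it.

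SE = 1.45 × √(1.09/148 + 1/n0), with clustering in the peer-support arm only and n0 usual-care patients. False-positive rate = 1 − Φ(1.96 − b/SE) + Φ(−1.96 − b/SE), where b is the residual offset. The available text gives no usual-care sample size, so n0 is varied:

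| n0 (assumed) | SE | Rate, b = 0.04 | Rate, b = 0.10 |
|---|---|---|---|
| 74 | 0.210 | 5.4% | 7.7% |
| 148 | 0.172 | 5.6% | 8.9% |
| 296 | 0.150 | 5.8% | 10.2% |
| 592 | 0.138 | 6.0% | 11.2% |

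The SD used is that of the change score. A smaller residual SD after baseline adjustment would raise these rates slightly. Timing effects cannot be sized from the documents.

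**Power of a CDW-in-both-groups analysis.** Let c be the share of the 174 enrolled peer-support patients with in-window CDW values at both baseline and follow-up. Then n = 174c. With 87 mentors over two arms, m = n/43.5 and DE = 1 + (m − 1) × 0.03. SE = 1.45 × √(DE/n + 1/n0). For a difference of 0.5 and n0 = n:

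| c (assumed) | n | DE | SE | Power |
|---|---|---|---|---|
| 85% | 148 | 1.072 | 0.172 | 83% |
| 72% (0.85 × 0.85) | 126 | 1.057 | 0.185 | 77% |
| 50% | 87 | 1.030 | 0.221 | 62% |

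The middle row applies if 85% holds independently at each of the two times. At 50% coverage, power is 72% with 148 usual-care patients and 80% with 296.

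**The case against.** The strongest reply is that the plan already covers much of this. It checks the DCA against a VA laboratory, may adjust for service use, and models who has outcome data before imputing. It also calls the comparison observational, so readers are warned. The illustrated bias rests on assumed inputs, is modest, and disappears in a plain change score.

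Much of that stands. A reader might infer that selection into testing is ignored. It is not: the service-use clause and the analyses in SAP 3.7 and 3.7.5 address it in part. A reader might also infer that the plan has no window or rule for choosing among CDW values. The documents do not support that either. The available Protocol text begins at the measures section and cites an earlier Section 3.4.1, so a rule may be stated elsewhere. Even a good window rule would leave DCA values set against CDW values.

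The remedy has limits too. The 85% figure is not tied to a 6-month window. The Protocol allows for outside care by recording "whether all diabetes care is received at VA". Study testing may also displace clinic testing, so missingness could differ by group. If the two analyses disagree, source, timing and the patients included will all have changed together.

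**Conclusion.** The point holds as a cheap improvement to a secondary, non-randomized comparison. A1c source and test timing are inseparable from group, and no stated covariate or missing-data analysis deals with the source or date of values that are present. The size and direction of any bias are unknown. The range of 5.6% to 8.9% rests on an assumed offset, assumed slopes and an assumed 148 usual-care patients, and is not an estimate.

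A reader might infer that the trial's primary result is compromised. It is not: the randomized comparison of technology-enhanced coaching with peer support alone uses DCA A1c in both arms. Nor would a common source make the usual-care comparison causal, since confounding would remain.

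**What to change.** For the comparison of peer support alone with usual care only:

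1. Prespecify, before outcome values are extracted, a companion sensitivity analysis using CDW A1c in both groups under one common index date and window rule. If the Protocol already contains such a rule, use it. If not, one form is the last value in a fixed window before the index date and the value nearest 6 and 12 months in a fixed window.
2. Treat out-of-window values as missing and pass them to the planned missing-data analyses.
3. Report by group the proportion with in-window CDW values at both baseline and follow-up and the distribution of test dates, beside the planned DCA-versus-CDW result.
4. Discuss any disagreement as showing dependence on how A1c was recorded, without attributing a cause. Do not require both intervals to exclude zero.

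Keep DCA A1c for the randomized comparison.

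The cost is one more extraction. CDW is already the source for usual care, and SAP 3.7 (Aim 3) already takes participants' most recent A1c from VA administrative data to describe reach, so access exists. The 6- and 12-month values would be new. The price in precision depends on coverage, as shown above, which is why this analysis should accompany the planned one.

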Attachment Style      1      Relationship Questionnaire[89]

Perceived Need for DM self-management support      1      Support Needs Scale from Diabetes Care Profile[90]

Perceived Benefits and Barriers to Taking DM medications      1      Two subscales from instrument assessing perceived barriers to and benefits from taking diabetes medications based on health beliefs model[91]

Health Literacy    1      Functional Health Literacy Screener[18]

Numeracy      1      Subjective Numeracy Scale (SNS)[92]

Food insecurity 1      Food Security Survey Module [93]

Neighborhood Safety, Availability of Healthy Foods, and Walking Environment 1      Neighborhood Safety Measure, Availability of Healthy Foods, Walking Environment [94]

\*Time point 1 is baseline, 2 is at 6 months, 3 is at 12 months.

We will measure standard demographic information including age, gender, and marital status. Socio-economic status (SES) will be measured using highest grade in school completed, income, and household size. We will collect data on diabetes duration and whether all diabetes care is received at VA and distance Veteran travels to Detroit VA. We will also collect data on any adverse symptoms experienced during the study period such as hypoglycemic symptoms or episodes, although have had no hypoglycemic episodes in our prior peer support interventions. Data on diabetes-related complications and other co-morbidities will be drawn from EMRs.
